7.6.4 Exposure to Concomitant Medication

Prior and concomitant medications and concomitant non-drug therapies, including the use of sunscreen, in addition to the reason for the medication use, will be assessed at baseline and at each subsequent study visit. The start and stop date of concomitant medication use during the study will be provided in the data set, in addition to the reason for the medication use.

Medication or non-drug therapy will be classified as prior, if the end date is known and is prior to the first use of the study medication. Medications and non-drug therapies that are ongoing or ended after the first use of the study medication will be classified as concomitant. If the end date of the medication or non-drug therapy is unknown, it will also be considered concomitant.

The concomitant medications will be summarized by preferred term for each treatment group as coded by the World Health Organization Drug (WHODRUG) dictionary Sept-2015 B2 and be listed in a by patient listings. Prior medications will be listed only.

8. CHANGES FROM PROTOCOL-SPECIFIED ANALYSES

There are no changes from the protocol-specified analyses.

9. LIST OF PLANNED TABLES, FIGURES, AND LISTINGS

See separate document with the table, figure and listing shells.

11. APPENDICES

11.1 Study visit Schedule

Visit Number	Visit 1	Visit 2	Visit 3	Visit 4
Visit Day	Day 0	Day 28±4	Day 56±4	Day 84±4
Visit Name	Baseline	Interim	Interim	End of Treatment/ Early Termination
Informed Consent	X			
Demographics	X			
Medical History	X			
Inclusion/Exclusion Criteria	X			
Physical Exam including Vital Signs	X			
Pregnancy Test *	X	X	X	X
Concomitant Medication	X	X	X	X
Adverse Event		X	X	X
Inflammatory Lesion Counts	X	X	X	X
Investigator's Global Evaluation (IGE)	X	X	X	X
Telangiectasia Assessment	X			
Irritation Assessment	X	X	X	X
Subject Instruction/Compliance Review	X	X	X	X
Dispense Study Medication and Diary **	X	X	X	
Collect Study Medication and Diary (Accountability)		X	X	X

* Urine pregnancy test for all females of childbearing potential enrolled in study.

** Day 1 will occur the date patient begins dosing. This may be the evening of Visit 1 or the following day.

11.2 IGE Scale

Score	Grade	Description
0	Clear	No inflammatory lesions present; at most, mild erythema
1	Almost Clear	Very mild erythema present. Very few small papules/pustules.
2	Mild	Mild erythema. Several small papules/pustules.

3	Moderate	Moderate erythema. Several small or large papules/pustules, and up to 2 nodules.
4	Severe	Severe erythema. Numerous small and/or large papules/pustules, up to several nodules.

11.3 Application Site Reactions Scores

Erythema:

Score	Grade	Definition
0	None	No redness present.
1	Very Mild	Slight pinkness.
2	Mild	Pink to light red.
3	Moderate	Definite redness, easily recognized.
4	Severe	Marked erythema; fiery red.

Dryness:

Score	Grade	Definition
0	None	No dryness.
1	Mild	Slight but definite roughness.
2	Moderate	Moderate roughness.
3	Severe	Marked roughness.

Scaling:

Score	Grade	Definition
0	None	No scaling.
1	Mild	Barely perceptible shedding, noticeable only on light scratching or rubbing.
2	Moderate	Obvious but not profuse scaling.
3	Severe	Heavy scale production.

Pruritus:

Score	Grade	Definition
0	None	No itching.
1	Mild	Slight itching but not bothersome.
2	Moderate	Definite itching, somewhat bothersome without loss of sleep.
3	Severe	Intense itching that has caused pronounced discomfort; interrupted sleep and excoriation of the skin may be present.

Stinging/Burning:

Score	Grade	Definition
0	None	No stinging/burning.
1	Mild	Slight warm tingling sensation but not bothersome.
2	Moderate	Definite warm tingling/stinging sensation somewhat bothersome.
3	Severe	Hot tingling/stinging sensation that has caused definite discomfort

Edema:

Score	Grade	Definition
0	None	No swelling.
1	Mild	Slightly or barely perceptible swelling.
2	Moderate	Distinct presence of swelling.
3	Severe	Marked or intense swelling.

11.4 Code Fragments

ANOVA model for superiority analysis in primary endpoint

```
proc glm data=<datasets name>;
  class <treatment> <center>;
  model <Percent change from baseline in lesion count at week 12> = <treatment> <center>
    <treatment>*< center>/ ss3;
  lsmeans <treatment> / pdiff cl;
```

```
      output out=residuals residual=residual;
run;
quit;
```

Note: this analysis needs to be performed separately for test and reference treatments on a dataset containing only test and vehicle or reference and vehicle treatment patients. If treatment-by-center interaction term is not significant at 0.05 level, the model will be rerun without this term.

Superiority analysis in secondary endpoint

```
proc freq data=<dataset>
  tables <treatment>*<success> / fisher;
run;
```

Note: this analysis needs to be performed separately for test and reference treatments on a dataset containing only test and vehicle or reference and vehicle treatment patients.

Analysis of clinical equivalence in primary endpoint

ANOVA model:

```
proc glm data=<datasets name>;
  class <treatment> <center>;
  model <Percent change from baseline in each type of lesions at week 12> = <treatment>
    <center> <treatment>*<center>/ ss3;
  lsmeans <treatment> / stderr;
  output out=residuals residual=residual;
run;
quit;
```

Here dataset contains test and reference treatment patients only.

Note: if the treatment-by-center interaction term is not significant at the 0.05 level, the model will be rerun without this term.

Fieller's method.

Generally, Fieller's formula allows to calculate the confidence interval for the ratio of two (possibly correlated) means of two samples a and b with expectations μ_a and μ_b , and variances $\nu_{11}\sigma^2$ and $\nu_{22}\sigma^2$ and covariance $\nu_{12}\sigma^2$. If ν_{11} , ν_{12} , ν_{22} are all known, then a $(1 - 2\alpha)$ confidence interval (mL, mU) for μ_a/μ_b is given by

$$(m_L, m_U) = \frac{1}{(1-g)} \left[\frac{a}{b} - \frac{g\nu_{12}}{\nu_{22}} \mp \frac{t_{r,\alpha}s}{b} \sqrt{\nu_{11} - 2\frac{a}{b}\nu_{12} + \frac{a^2}{b^2}\nu_{22} - g \left(\nu_{11} - \frac{\nu_{12}^2}{\nu_{22}} \right)} \right]$$

where

$$g = \frac{t_{r,\alpha}^2 s^2 \nu_{22}}{b^2}.$$

Here s^2 is an unbiased estimator of σ^2 based on r degrees of freedom, and $t_{r,\alpha}$ is the α -level deviate from the Student's t-distribution based on r degrees of freedom.

In the case of this study the two samples are independent (different patients), thus covariance can be assumed to be zero, and the formula simplifies to:

$$(m_L, m_U) = \frac{1}{1-g} \left[\frac{m_t}{m_r} \mp \frac{t_{r,\alpha}}{m_r} \sqrt{s e_t^2 + \frac{m_t^2}{m_r^2} s e_r^2 - g \cdot s e_t^2} \right]$$

where

$$g = \frac{t_{r,\alpha}^2 s e_r^2}{m_r^2}$$

Here m_t and $s e_t$ are mean and standard error estimate for test treatment and m_r and $s e_r$ for reference treatment correspondingly obtained from the above model. The degrees of freedom r can be obtained from the model as degrees of freedom for the error term in the overall ANOVA table, $\alpha = 0.05$ (for the 90% confidence interval). The term $t_{r,\alpha}$ can be calculated in SAS as $\text{tinv}(\alpha, r)$.

Clinical equivalence analysis in secondary endpoint

```
proc freq data=<dataset>
  tables <treatment>*<success> / riskdiffc;
run;
```

Note: this analysis needs to be performed on a dataset containing test and reference treatment patients only.

Evaluation of skewness

This evaluation will be performed on the residuals output by the "output" statement in PROCGLM above:

```
proc univariate data=residuals;
  var residual;
run;
```

Non-parameteric rank ANOVA

If decision to use the rank ANOVA is taken, the data will be ranked first:

```
proc rank data=<dataset>
  var <change_from_baseline>;
  ranks rank;
run;
```

After that the analysis will proceed using the same SAS code as described above but using rank variable instead of the original change from baseline.

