Statistical Methods:	
Analysis of Primary Endpoint
 
The percent change from baseline to Week 12 in the inflammatory (papules and pustules) lesion counts is the primary endpoint for the study. A LOCF approach will be used for imputation of missing efficacy results, where appropriate.
 
Demonstration of Bioequivalence
 
A two-way ANOVA on the test and reference results for the primary endpoint will be conducted using a statistical model containing terms for treatment and site. Bioequivalence for the primary endpoint will be established if the 90% confidence interval for the test/reference ratio of the mean percent change from baseline to Week 12 in the inflammatory (papules and pustules) lesion counts is contained within [0.80, 1.25], using the PP population. Non-parametric methods will be used if the skewness factor for the residuals from the ANOVA model are outside the range -2 to +2.
 
Demonstration of Superiority
 
To ensure that the study is sensitive enough, the test product and reference listed drug (RLD) will each be compared to the vehicle group to demonstrate their statistical superiority at $p<0.05$ (two sided) for the primary endpoint, using the mITT study population. This evaluation will be performed using separate two-way ANOVA of Test vs. Vehicle and Reference vs. Vehicle, with the statistical model containing terms for treatment and site. Non-parametric methods will be used if the skewness factor for the residuals from the ANOVA model are outside the range -2 to +2.
 
Analysis of Secondary Endpoint
 
The dichotomized Investigator's Global Evaluation (IGE) will be treated as a secondary endpoint for supportive evidence. This secondary endpoint will be evaluated as the proportion of patients with a clinical response of "success" at Week 12. Success is defined as an either IGE score 0 (clear) or 1 (almost clear) at the final visit. Any patient who is not considered a success will be considered to be a failure. A LOCF approach will be used for imputation of missing efficacy results, where appropriate.
 
Demonstration of Bioequivalence
 
Bioequivalence for the secondary endpoint will be established if the 90% continuity-corrected confidence interval for the difference in clinical

success proportions between the test and reference product is contained within the interval [-0.20, +0.20] for the PP population.

Demonstration of Superiority

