12.5.2 Analysis of Secondary Endpoint

Demonstration of Bioequivalence

Bioequivalence for the secondary endpoint, will be established if the 90% confidence interval, Wald's method with Yate's continuity correction, for the test-to-reference difference in IGE success proportions is contained within the interval [-0.20, +0.20] in the PP population. An identical analysis will be conducted on the mITT population to test for the robustness of the findings for the PP population. A LOCF approach will be used for missing efficacy results in the mITT analysis.

Demonstration of Superiority

The evaluation of the superiority of the test treatment over the vehicle treatment for the proportion of patients with success on the IGE at Week 12 will be conducted using Fisher's exact test. If the success proportion for the test treatment is greater than, and statistically different from ($p<0.05$) that of the vehicle in the mITT population, then the test product will be considered superior to the vehicle. The results for the reference treatment will be compared to those for the vehicle in an identical manner. The same analyses will be conducted for the results from the PP population to test for robustness of the findings in the mITT population. A LOCF approach will be used for missing efficacy results in the mITT analysis.

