5. HYPOTHESES TESTING

Hypothesis of Equivalence (Primary Endpoint)

A two-sided, 90% confidence interval on the test/reference ratio for mean percent change from Baseline in the inflammatory lesion count will be constructed using Fieller's method. The estimates of treatment means and standard errors will be obtained from a two-way Analysis of Variance of the Test and Reference results, using a statistical model containing terms for treatment and center. Non-parametric methods will be used if the skewness factor for the residuals from the Analysis of Variance (ANOVA) model is outside the range -2 to +2. Bioequivalence will be established if the 90% confidence interval for the ratio of test/reference means is contained within the interval [0.80, 1.25].

Hypothesis of Equivalence (Secondary Endpoint)

A two-sided, continuity-corrected, 90% confidence interval on the Test-to-Reference difference for the proportion of patients with treatment success on the IGE will be constructed. Bioequivalence will be established if the 90% confidence interval for the difference is contained within the interval [-0.20, +0.20].

Hypothesis of Superiority (Primary Endpoint)

The null hypothesis to be tested is that there is no difference in the mean percent change (reduction) from baseline in the inflammatory lesion count between the active treatment and the Vehicle treatment. The hypothesis testing will be performed separately for the Test treatment versus the Vehicle treatment and for the Reference treatment versus the Vehicle treatment using ANOVA under assumption of normal error and homogeneity of variance. Only data for the relevant two treatment arms will be included in each ANOVA. Similarly, to bioequivalence, non-parametric methods will be used if the skewness factor for the residuals from the ANOVA model is outside the range -2 to +2.

Superiority will be established if the mean percent change (reduction) from Baseline in the inflammatory lesion count for each active treatment is greater than, and statistically different from ($p < 0.05$, two-sided), that for the Vehicle.

Hypothesis of Superiority (Secondary Endpoint)

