7. STATISTICAL METHODS OF ANALYSIS

7.1 General Principles

The statistical analyses will be performed by [REDACTED], under the direction of the Sponsor, Actavis Laboratories UT, using SAS Version 9.3(or higher). All tables, figures, and listings will be produced in the landscape format.

In general, all data will be listed by treatment group, patient and visit/time point where appropriate. The summary tables will also be stratified by, or have columns corresponding to, treatment group.

All patients will be identified by their unique patient numbers. Data from the screen failures will not be included in tables, listings, or figures.

The total number of patients in the study group (N) under the stated population will be displayed in the header of summary tables.

Data will be summarized using descriptive statistics for continuous variables. Unless otherwise stated, descriptive statistics will include number of patients, mean, standard deviation, minimum, median, and maximum. The minimum and maximum statistics will be presented to the same number of decimal places as the original data. The mean and median will be presented to one more decimal place than the original data. The standard deviation will be presented to two more decimal places than the original data. The number of missing observations will be presented only if non-zero.

In summary tables of categorical variables, counts, and percentages will be used. The count [n] indicates the actual number of patients in a particular category, which should always be less than or equal to the total number of patients in the respective study group with known (non-missing) category [N]. Percentage will be obtained by: $\% = n/N*100$. Unless otherwise stated, all percentages will be expressed to one decimal place.

All statistical tests will be two-sided at a significance level of $\alpha = 0.05$, unless otherwise indicated. No adjustment will be made for multiplicity.

Relative days will be calculated relative to date of first dose of study medication. In general, relative days will be calculated as follows only when the full assessment date is known (i.e., partial dates will have missing relative days).

For assessment on or after the day of first dose of study drug:

Relative Day = Date of Assessment – Date of First Dose of study Drug+1.

For assessment before the day of first dose of study drug:

Relative Day = Date of Assessment – Date of First Dose of study Drug.

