7.5.3.1 Analysis of clinical equivalence of test and reference treatments

A two-sided, continuity-corrected, 90% confidence interval on the Test-to-Reference difference for the proportion of patients with treatment success on the IGE will be constructed. Bioequivalence will be established if the 90% confidence interval for the difference is contained within the interval [-0.20, +0.20] for the PP population.

Analysis of bioequivalence will be performed both on the PP population and on the mITT population. The results on the PP population will be considered definitive and the results on the mITT population supportive.

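### The SAP 11.4 code for the IGE equivalence interval sets no confidence level; completed without one, it returns 95% limits where the plan requires 90%

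*SAP*

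**What the plan says.** The required level is the same in four places: the Protocol synopsis (statistical methods), Protocol 12.5.2, SAP 5 and SAP 7.5.3.1. Protocol 12.5.2 begins its rule "Bioequivalence for the secondary endpoint, will be established if the 90% confidence interval", names the Wald method with continuity correction, and sets the limits at ±0.20 in the PP population. SAP 7.5.3.1 calls for "A two-sided, continuity-corrected, 90% confidence interval on the Test-to-Reference difference for the proportion of patients with treatment success" on the IGE, with the same limits. The synopsis says that the dichotomized IGE "will be treated as a secondary endpoint for supportive evidence".

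The code for this interval is in SAP 11.4, under the clinical equivalence analysis of the secondary endpoint. Its operative statement is "tables <treatment>*<success> / riskdiffc". The note beneath reads "Note: this analysis needs to be performed on a dataset containing test and reference treatment patients only" and says nothing about the level.

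For the other equivalence interval, the Fieller interval for lesion counts, the same appendix does give the level in prose beside the formula: α = 0.05, "for the 90% confidence interval". SAP 8 states that nothing departs from the protocol's analyses.

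**The concern.** SAP 11.4 is the plan's own code for this step, and the one setting that fixes the width of the interval is absent. PROC FREQ uses a two-sided alpha of 0.05 when none is given, so the completed fragment would print 95% limits. If those are compared with ±0.20, the verdict comes from a wider interval than the one pre-specified.

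At stake is a wrongly failed IGE equivalence verdict, or a code correction after unblinding that then has to be explained. The fault is easy to repeat. The Fieller section uses a per-side α of 0.05 to obtain a 90% interval, but a programmer who carried 0.05 over to PROC FREQ would still get 95%, because alpha there is two-sided.

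**Working it through.** **Level.** Required: 90%, so two-sided alpha = 0.10 and z = 1.645. Given by the completed fragment: 1 − 0.05 = 95%, z = 1.960. The ratio of multipliers is 1.960/1.645 = 1.19.

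The SAP's own usage is consistent with that default. Its superiority code in 11.4 asks for least-squares-mean limits with no alpha, and SAP 7.5.2.2 calls those limits 95%. That is a different SAS procedure, so this supports the reading but does not prove it.

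**Inputs.**
- n = 224 PP patients per arm (Protocol 11.2 and 12.1; SAP 3.1 and 3.2).
- Limits of ±0.20 (Protocol 12.5.2; SAP 5 and 7.5.3.1).
- IGE success rate: not in the documents. 40% is assumed for the reference arm, and 30% to 60% is shown as a range.

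**Formula.** Half-width = z × √[pT(1−pT)/n + pR(1−pR)/n] + ½(1/n + 1/n). The last term is 1/n = 0.0045 at n = 224. The result passes if both limits lie within ±0.20.

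**One result in full: 115/224 on test, 90/224 on reference.**
- pT = 0.5134, pR = 0.4018, difference 0.1116.
- Standard error = √(0.5134×0.4866/224 + 0.4018×0.5982/224) = 0.0468.
- 90%: half-width 1.645×0.0468 + 0.0045 = 0.0814; limits 0.030 to 0.193, pass.
- 95%: half-width 1.960×0.0468 + 0.0045 = 0.0961; limits 0.016 to 0.208, fail.

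**Band in which the verdict changes, reference fixed at 90/224, test above reference.**

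| Test successes | Difference | Upper 90% limit | Upper 95% limit |
|---|---|---|---|
| 113 | 0.103 | 0.184, pass | 0.199, pass |
| 114 | 0.107 | 0.189, pass | 0.203, fail |
| 115 | 0.112 | 0.193, pass | 0.208, fail |
| 116 | 0.116 | 0.197, pass | 0.212, fail |
| 117 | 0.121 | 0.202, fail | 0.217, fail |

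The same formula with test below reference changes the verdict at test counts 63 to 65. For example, 64/224 gives a difference of −0.116, a lower 90% limit of −0.194 and a lower 95% limit of −0.208.

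**Probability of passing**, by exact enumeration of all pairs of success counts:

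| n per arm | Reference rate | True difference | 90% limits | 95% limits |
|---|---|---|---|---|
| 224 | 0.40 | 0 | 0.990 | 0.977 |
| 224 | 0.40 | +0.05 | 0.929 | 0.880 |
| 224 | 0.30–0.60 | 0 | 0.988–0.996 | 0.974–0.990 |
| 224 | 0.30–0.60 | ±0.05 | 0.926–0.966 | 0.878–0.933 |
| 210 | 0.40 | +0.05 | 0.917 | 0.861 |
| 280 | 0.40 | +0.05 | 0.969 | 0.943 |

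The 210 is 0.75 × 280, from the 75% PP fraction anticipated in Protocol 12.1 and SAP 3.2. The 280 is the supportive mITT analysis.

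**Direction.** The 95% interval always contains the 90% interval. Enumeration at n = 210, 224 and 280 found no pair that passes at 95% and fails at 90%. At a true difference of +0.20 with a 40% reference rate and n = 224, the chance of falsely declaring equivalence is 0.039 with 90% limits and 0.020 with 95% limits.

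**The case against.** The strongest reply is that the plan is not in doubt. Four passages state 90% and none states 95% for this interval. The appendix holds code fragments with placeholders, and the PROC FREQ line has no closing semicolon in the text available, so nothing in it runs literally. A programmer has to complete it from the SAP text and should take the level from SAP 7.5.3.1. The Fieller level, too, is given in prose and not in code. The table shells are a separate document (SAP 9) and may state 90%.

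Much of this stands. The analysis is fully specified, and the defect is an omitted option. What does not follow is that the omission is harmless. Filling in placeholders does not supply an alpha, and a correct result should not depend on someone noticing that the plan's code needs an option it does not show.

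Three stronger readings are tempting and are not supported:
- **That SAP 7.1 sets a competing level.** It says "All statistical tests will be two-sided at a significance level of" 0.05, but it excepts cases where another level is indicated. SAP 5 and 7.5.3.1 indicate 90% for this interval, so there is no conflict.
- **That the error could let non-equivalent products pass.** The wider interval makes passing harder, never easier.
- **That the trial's main conclusion or planned power is at risk.** The lesion-count equivalence analysis uses Fieller limits with the level stated. The documents give no power target for the IGE, and the synopsis calls it supportive.

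**Conclusion.** The point holds as a mismatch between code and text, and it is minor. The SAP text is unambiguous at 90%. The 11.4 fragment, completed without a level, gives 95%.

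The effect is conservative and confined to the supportive IGE endpoint. With 90 reference successes and test above reference, three test counts change verdict. At an assumed 40% success rate, the loss of power is about 1.3 percentage points at no true difference (0.990 − 0.977) and about 4.9 points at +0.05 (0.929 − 0.880).

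This rests on two things outside the documents: the PROC FREQ default, which is a known property of the software, and the assumed IGE success rates. The rates affect only the size of the effect. The finding concerns the appendix alone; the table shells could not be checked.

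**What to change.** In the SAP 11.4 fragment for the IGE equivalence analysis, change the options after the slash to `riskdiffc alpha=0.10`. Add to the note beneath it: the limits compared with ±0.20 are the two-sided 90% continuity-corrected limits. Confirm that the table shells carry the same level.

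The cost is one SAS option and one sentence, both in the SAP and best made before unblinding. The method, protocol, data collection and sample size do not change, and the SAP 8 statement of no departures is unaffected.
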